8.8.4 Individual Subject Study Drug Dosing Discontinuation

Dosing of cePolyTregs will be permanently discontinued in a study subject if any of the following occur:

- Any DLT
- Subject withdraws consent
- Pregnancy
- Subject is unable to comply with the protocol requirements
- Sponsor terminates the study

- A regulatory authority mandates dosing cessation

In all cases, necessary measures will be taken to ensure appropriate safety follow-up of all subjects in the trial.

8.8.5 Subject Replacement

Subjects experiencing a product-related DLT will discontinue dosing and be asked to remain in the study and complete all study visits through the EOS visit; these subjects will not be replaced. If a subject terminates early for a reason other than a toxicity during the Treatment Period, the subject may be replaced at the discretion of the Sponsor.

8.8.6 Study Discontinuation

The study may be stopped at the discretion of the Sponsor based on recommendations of the DSMB. The study may also be stopped pending DSMB evaluation of all available safety and PD data if any of the following occur:

- Any study drug-related death
- The occurrence of 3 deaths within 28 days post treatment in the first 5 subjects treated or, subsequent to the first 5 subjects, the observed mortality rate across the cumulative population of treated subjects exceeds the anticipated mortality rate of 50%
- Two CTCAE Grade 4 or 5 TEAEs that are deemed related to study drug
- An increase in the incidence of infections of special interest (pneumonia or infections involving pathogens not anticipated in a COVID-19 setting) beyond the expected background incidence

If the DSMB recommendation is to interrupt study dosing for all subjects or to pause enrollment, study dosing can be resumed, based on the recommendation of the DSMB, only after further review of all available safety data and applicable notifications of submission to appropriate regulatory agencies and institutional review committees, in line with country-specific regulations.

All deaths occurring during the study will be reviewed promptly by the DSMB as they occur. If at any point following enrollment of the first 5 subjects, the observed mortality rate across the cumulative population of treated subjects exceeds the anticipated mortality rate of 50%, the study will be halted.

9 STUDY POPULATION

Each cohort will enroll unique subjects who may not be treated in more than 1 cohort.

9.1 Inclusion Criteria

1. Diagnosis of ARDS and respiratory failure requiring mechanical ventilation for less than 72 hours at the time of enrollment
2. $\text{PaO}_2/\text{FiO}_2 < 300$ and PEEP > 5
3. Male or female, age 18 to 70 years at Screening
4. Weight > 40 kg
5. Documented diagnosis of infection with SARS-CoV-2 virus by PCR
6. Chest imaging (radiograph or CT scan) with abnormalities consistent with COVID-19 pneumonia that could not be explained by effusions, pulmonary collapse, or nodules; and respiratory failure that could not be explained by cardiac failure or fluid overload
7. Females of childbearing potential and males must use effective contraception practices from Screening until 28 days after the EOS visit
8. Females of childbearing potential must have a negative pregnancy test at Screening and within 24 hours prior to dosing of study drug
9. Able to provide Informed Consent, either by self or by medical proxy
10. Willing and able to comply with this protocol for the entire duration of the study

9.2 Exclusion Criteria (Parts 1 and 2)

Subjects will be ineligible for enrollment in the study if they meet any of the following criteria:

1. Any history or sign of significant chronic active or recurrent infection or screening laboratory evidence consistent with a significant chronic active or recurrent infection requiring treatment with antibiotics, antivirals or antifungals (other than SARS-CoV-2); ongoing antimicrobial treatments will not be exclusionary if, in the opinion of the investigator, no active infection is present (other than SARS-CoV-2)
2. Receiving extracorporeal membrane oxygenation therapy
3. Moribund patients not expected to survive 24 hours after enrollment based on clinical assessment
4. History of significant underlying pulmonary disease (requiring home oxygen), renal disease (requiring dialysis for chronic kidney disease), hepatic disease (Child-Pugh score ≥ 7), or known history of cirrhosis.
5. Known or suspected immunodeficiency disease
6. Positive serology for HBV, HCV, or HIV at Screening

UCSF	Clinical Study Protocol No. UCSF-cePolyTregs-01	Page 39 of 72
------	---	---------------

7. Abnormal CBC defined by:
 - a. Platelet count < 75,000/mm³
 - b. White blood cell count < 2500/mm³
 - c. Absolute neutrophil count < 500/mm³
8. History of bone marrow or stem cell transplantation
9. Received any type of live attenuated vaccine < 1 month prior to Screening or is planning to receive any such live attenuated vaccine over the course of the study
10. History of lung cancer or any other malignancy requiring active treatment, except adequately treated basal cell carcinoma or in situ carcinoma of the uterine cervix
11. Any female who is pregnant or breastfeeding, or any female who is planning to become pregnant during the study and follow-up period
12. Any condition that, in the investigator's opinion, may compromise study participation, present a safety risk to the subject, or may confound the interpretation of the study results
13. A QT duration corrected for heart rate by Fridericia's formula (QTcF) > 450 millisecond (msec) for males or > 470 msec for females, based on either single or averaged QTcF values of triplicate ECGs obtained over a 3-minute interval
14. Currently enrolled in another investigational device or drug study
15. Greater than 10 days of continuous (>12 hours/day) administration of oxygen via non-invasive positive pressure ventilation or high-flow nasal cannula oxygen for hypoxemic respiratory failure due to COVID-19

10 STUDY TREATMENTS

10.1 Description of Treatments

Detailed information regarding the storage, preparation, and administration of cePolyTregs and placebo for this study is contained in the cePolyTregs Cell Therapy Manual.

All subjects in both parts of the study will receive standard of care treatment for COVID-19, including dexamethasone per institutional guidelines and other approved therapies for ARDS associated with SARS-CoV-2 infection per institutional guidelines.

In addition, all subjects in the Part 1 cohorts will receive open-label cePolyTregs. All subjects in the Part 2 cohorts will be randomized in a blinded fashion to receive either cePolyTregs or matching placebo using a 1:1 (active:placebo) allocation ratio.

The study drugs are:

- cePolyTregs containing polyclonal Treg cells that have been collected from qualified donors by leukopheresis under GMP conditions, purified to yield a population of CD4⁺CD127^{lo/-}CD25⁺ regulatory T cells, expanded using anti-CD3/anti-CD28-coated magnetic microbeads and IL-2 for 12 to 13 days, debeaded and cryopreserved in Cryostor[®] CS5 solution at a concentration of 1x10⁷ cells/mL.
- Placebo, containing an inactive substance designed to mimic the excipient of the investigational product, at a matched volume to the cePolyTregs infusion.

Planned single doses of cePolyTregs in Part 1 of the study are as follows:

- 1 x 10⁸ cells by manual IV infusion;
- 2 x 10⁸ cells by manual IV infusion;
- 4 x 10⁸ cells by manual IV infusion

Single doses of cePolyTregs in the placebo-controlled Part 2 of the study will be determined based on the results observed in Part 1.

10.2 Packaging and Labeling

cePolyTregs are cryopreserved in either CryoMACS[®] Freezing Bag 50 or CryoMACS[®] Freezing Bag 250 depending on the dose. The CryoMACS[®] Freezing Bag consists of a freezing bag and corresponding overwrap bag. Both the freezing bag and overwrap bags are composed of ethylene vinyl acetate tubular film and are individually packed and sterilized.

cePolyTregs are distributed to clinical study sites and stored in liquid nitrogen until use.

cePolyTregs will be labeled by the manufacturing site with product information including: product name and identifiers, method of manipulation, formulation, source cell material details,

date of cryopreservation, storage instructions, and all applicable statements and warnings. Product will be issued to each subject by the clinical site prior to infusion.

LHTR-CNNN - XXX-BB
Source cells Collection Facility:
Full Facility Name, Street Address,
City, State ZIP
Collection end date/Time/Time
Zone
DD-MMM-YYYY HH:MM ie.PT
Donor Number: #####

WARNING: Advise Patient of
Communicable Disease Risks
WARNING: Reactive Test Results for
CMV [if applicable]
Caution: New Drug – Limited by
Federal Law to Investigational Use

DO NOT IRRADIATE
DO NOT USE LEUKOREDUCTION
FILTERS
Store below -130°C 

**Cryopreserved Ex Vivo Expanded
Polyclonal CD4⁺CD127^{lo}/CD25⁺ T
Regulatory Cells**

Contains XXX x10⁶ cells in ## mL of
CryoStor[®] CS5

Cryopreserved on DD-MMM-YYYY

Method of manipulation: [12 or
13] day Ex Vivo polyclonal
expansion using anti-CD3/anti-
CD28 expansion beads and IL-2.
Manufactured and Processed by
UCSF HICTF and GMP Facility
[name],
94103, USA
FDA Registration # FEI3005404215

As is generally the case with blood products and cellular therapies, the labels on the cePolyTregs bags and the placebo bags will be different and will need to be checked at bedside as part of the infusion process. Consequently, study product identity will be blinded for the subjects and investigators but will not be blinded for other site staff.

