8.1.2 Part 2 (Phase 2a)

Part 2 is a double-blind, randomized, placebo-controlled parallel group study of a single IV administration of the RP2D of cePolyTregs compared to placebo/SOC. Dose selection for Part 2 will be based on determination of the RP2D from Part 1. Part 2 will consist of 2 cohorts (cePolyTregs and placebo/SOC) randomized 1:1, with randomization stratified by study site and baseline WHO severity scale for COVID-19 pulmonary syndrome. A total of 100 subjects are anticipated for randomization.

For both parts of the study, written informed consent for study participation will be obtained before any study-related procedures or assessments are performed. All potential subjects will be screened for potential participation, and those meeting all eligibility criteria will be offered participation in the study.

Subject participation in the study will be conducted in the 3 defined periods described in Sections [8.1.3](#) to [8.1.5](#).

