8.3 Rationale for Study Design

Part 1 of this study will be an open-label, dose escalation trial. On-treatment safety and changes in PD measures will be monitored to determine the safety of cePolyTregs and identify the RP2D for further study in Part 2. Safety and tolerability of cePolyTregs will be evaluated by continuous assessment of AEs, vital signs, ECGs, clinical laboratory parameters, and chest imaging. The PD and biomarker profile associated with cePolyTregs will be evaluated through serial blood sampling. Dose escalation will occur by cohort following review of data by the DSMB to allow emerging safety, PD, and other data to inform dose escalation decisions based on pre-defined DLT criteria and stopping rules.

Part 2 of this study has a randomized, double-blinded, placebo-controlled design to minimize bias in allocation of subjects to treatment assignment and evaluation of safety and clinical activity.

These design features are intended to minimize risk to subjects and to allow exploration of a safe range of doses over relatively short treatment duration as well as to explore doses associated with PD and clinical activity.

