10.3 Study Drug Dosage Preparation

cePolyTregs will be kept in a monitored freezer in vapor phase liquid nitrogen (LN₂) until the time of infusion. Stability after thawing is 4 hours. The long-term stability of cePolyTregs in LN₂ freezers is provided in the current Investigator's Brochure.

cePolyTregs will be prepared and administered under sterile conditions according to the Cell Therapy Manual. The cells will be thawed at the bedside using a water bath or comparable device maintained at 34°C to 38°C by trained personnel. There should be no frozen clumps left in the container at the time it is infused. If the cePolyTregs cell product appears to be damaged or the bag appears to be compromised, it should not be infused, and the site should notify HICTF and the GMP facility immediately.

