10.7 Enrollment or Randomization and Blinding

It is the investigator's responsibility to ensure that subjects are eligible to participate in the study prior to enrollment and continue to remain eligible throughout the study.

In Part 1 of the study, subjects will be enrolled and treated with open-label cePolyTregs sequentially in the order in which they are screened.

In Part 2 of the study, subjects will be assigned a subject identification number after the informed consent is signed using a centralized interactive web response system (IWRS) or other secure methodology. At randomization (Day 0), a centralized schema will be applied to randomize subjects in a 1:1 ratio to cePolyTregs or placebo. The system will stratify the randomized subjects by study site. All subjects and investigators will be blinded to treatment group throughout Part 2 of the study. Other study center staff will not be blinded because of differences in the product labels for active vs placebo product (see Section [10.2](#)). The investigator may request emergency unblinding for safety reasons; subjects unblinded for safety reasons should continue in the study for assessment of outcomes. Subjects who are randomized but do not receive study drug may be replaced.

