If any of the goals a. to e. are not met, revert to previous ventilator settings or to PS \geq 10 cm H₂O with Positive End-expiratory Pressure and FiO₂ = previous settings and reassess for weaning the next morning. The subject will be reassessed for weaning the following day.

Decision to remove ventilatory support:

If tolerance criteria for spontaneous breathing trial (a. to e. above) are met for at least 30 minutes, the clinical team may decide to discontinue mechanical ventilation. However, the spontaneous breathing trial can continue for up to 120 minutes if tolerance remains in question.

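### Part 2 blinding exempts more site staff than the bag-label reason justifies, and nothing keeps unblinded staff away from the weaning, oxygen step-down and scoring that determine recovery

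*Combined protocol and SAP*

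**What the plan says.** Section 8.1.2 gives the label: "Part 2 is a double-blind, randomized, placebo-controlled parallel group study of a single IV administration of the RP2D". Section 8.3 gives the purpose, a "design to minimize bias in allocation of subjects to treatment assignment and evaluation of safety and clinical activity".

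Two sections then define who is blinded. Section 10.2 explains that the labels on active and placebo bags "will be different and will need to be checked at bedside as part of the infusion process", and concludes that "study product identity will be blinded for the subjects and investigators but will not be blinded for other site staff". Section 10.7 repeats the rule and the reason: "Other study center staff will not be blinded because of differences in the product labels for active vs placebo product".

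On handling, section 10.3 states: "The cells will be thawed at the bedside using a water bath or comparable device". Section 10.4 has the cells drawn into a 60 mL syringe and infused by hand. Neither section mentions a cover or screen; both 10.1 and 10.3 refer to a Cell Therapy Manual for detail.

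On the endpoint, section 13.1 counts recovery as the first day within 28 days in WHO category 0 to 4. Section 9.1 admits only ventilated subjects. Section 11.13 places weaning under protocol rules so that methods are similar in both groups. Appendix B sets daily readiness criteria and breathing-trial tolerance criteria; once tolerance has lasted at least 30 minutes, "the clinical team may decide to discontinue mechanical ventilation".

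**The concern.** The reason for breaking the blind is that someone must read the bag label at the bedside. That accounts for the people who receive, thaw, check and infuse the product. It does not account for other staff at the center, yet both sections are worded to include them.

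This matters because the primary endpoint is partly a care decision. A subject who enters on a ventilator recovers only after someone stops ventilation and someone then steps the subject down to mask or nasal prongs. If a person making or shaping those decisions knows the allocation, the recovery day can move in one arm and not the other. The log-rank test cannot tell that from a treatment effect, and no analysis can repair it afterwards.

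**Working it through.** **1. Reason against rule.** The label check, thaw and syringe infusion (10.2 to 10.4) expose identity to product handlers and to anyone watching. The rule in 10.2 and 10.7 exempts site or study center staff other than investigators, without naming a handling team. No section bars an unblinded person from weaning, oxygen decisions or WHO and SOFA scoring. Section 11.6 names no assessor for the WHO scale.

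**2. Where discretion remains.** On the WHO scale in 11.6, subjects enter at 6 or 7 and must reach 4.
- From 6 or 7 to 5: Appendix B fixes the readiness screen and the tolerance limits. What remains is whether to stop ventilation after at least 30 minutes of tolerance or to continue the trial, up to 120 minutes. The clinical team decides.
- From 5 to 4: leaving high-flow oxygen for mask or prongs is the step that defines recovery. Appendix B has no rule for it.

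**3. The plan's own power figure.** Inputs from 13.2: medians 31.4 and 16 days, 50 per arm, two-sided 10%.
- Rate ratio: 31.4/16 = 1.96.
- Recovered by Day 28: 1 - exp(-28 ln 2/31.4) = 46.1%, and 1 - exp(-28 ln 2/16) = 70.3% (the plan prints 70.2%).
- Expected recoveries: 50 x 0.461 + 50 x 0.703 = 58.2.
- Schoenfeld: (sqrt(58.2)/2) x ln 1.96 = 2.57; 2.57 - 1.645 = 0.93; power 82.3%. Freedman's formula gives 79.8%, and simulation with 10,000 replicates gives 81.9%.

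The stated 80% is therefore reproduced, and the same model can carry the illustration.

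**4. Illustration of bias.** No true effect: both arms have the 31.4-day median. Recovery is recorded by day, and subjects not recovered by Day 28 are censored. An assumed distortion is then applied to the active arm only (4,000 replicates each; Monte-Carlo standard error 0.3 to 0.7 points).

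| Assumed distortion in active arm | Significant, favoring cePolyTregs | Significant, either direction |
|---|---|---|
| None | 5.1% | 9.8% |
| Recovery 1 day earlier | 6.4% | 10.0% |
| Recovery 2 days earlier | 9.0% | 11.4% |
| Recovery 3 days earlier | 11.3% | 13.5% |
| Recovery rate x 1.1 | 10.1% | 12.3% |
| Recovery rate x 1.2 | 16.1% | 17.3% |
| Recovery rate x 1.3 | 22.8% | 23.2% |

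Check by formula, drift = (sqrt(D)/2) x ln r, where D is the expected number of recoveries:
- r = 1.2: active-arm recovery 1 - 0.539^1.2 = 52.4%; D = 50 x (0.461 + 0.524) = 49.2; drift 0.64; P(Z > 1.645 - 0.64) is about 16%.
- r = 1.3: 1 - 0.539^1.3 = 55.2%; D = 50.7; drift 0.93; about 24%.

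To put the ratios on a day scale, 31.4/1.1 = 28.5, 31.4/1.2 = 26.2 and 31.4/1.3 = 24.2, so the active-arm median comes forward by 2.9, 5.2 and 7.2 days.

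**The case against.** A reader might infer that everyone at the site except the investigator, including the bedside team that extubates, knows the allocation. The documents do not support that. Both sections tie the unblinding to the labels, and so can be read as covering only staff who see them. Appendix B's clinical team is nowhere identified with the unblinded staff. The link is possible but not stated. What stands is that nothing excludes it either.

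The weaning protocol is a real safeguard. Discretion over extubation begins only after numeric readiness and tolerance criteria are met, and the WHO category largely records the device in use. This narrows the exposure, though it does not reach the step from category 5 to 4 or say who may know the allocation.

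A reader might also extend the point to adverse-event attribution. Section 12.5 gives causality to the investigator or a qualified sub-investigator, and 13.6 has the investigator grade events. Investigators are blinded, so attribution is not part of this point.

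Finally, the larger error rates should not be read as the trial's actual error. Ratios of 1.2 and 1.3 mean a distortion sustained in the whole active arm for 28 days, worth 5 to 7 days on the median, and nothing in the documents suggests one of that size. The sponsor also discloses the limitation openly, and the Cell Therapy Manual, which is not among the documents, may already specify masking.

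**Conclusion.** The point holds as a gap in the protocol's wording and safeguards. Sections 10.2 and 10.7 exempt more staff from blinding than the label reason requires, and no text separates unblinded staff from decisions that set the recovery day. The protection claimed in 8.3 for the evaluation of clinical activity is therefore not assured. The documents do not show that it fails.

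The amount of bias cannot be derived from them. Under the plan's exponential control rate with no true effect, the chance of a significant result favoring cePolyTregs goes from about 5% to 6-11% for recovery brought forward by 1 to 3 days, and to about 10-23% for a recovery-rate ratio of 1.1 to 1.3. All these distortions are assumed. The smaller ones seem easier to reconcile with daily protocolized weaning. The sponsor should settle this before Part 2 opens.

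**What to change.** In 10.2 and 10.7, limit unblinding to the staff who receive, thaw, label-check and infuse the product. Record in the delegation log that, for that subject and through Day 28, these people do not perform weaning screens, take part in extubation or oxygen step-down decisions, or score the WHO scale or SOFA. Those tasks stay with the blinded investigator and with existing staff not involved in the infusion.

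Shield the bag and syringe from view at the bedside, in a way that fits the bedside thaw and label check and agrees with the Cell Therapy Manual. The placebo is normal saline in the Synopsis but an excipient-mimicking substance in 10.1. The two should be reconciled, since the placebo's appearance affects how well shielding works.

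The change concerns who may decide and score, not the clinical criteria for weaning or oxygen. It leaves sample size, alpha and endpoint untouched and needs no added assessor. The cost is protocol wording, a delegation-log entry and a modest rostering restriction that lasts the 28-day window, not just the infusion day.

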10.3 Study Drug Dosage Preparation

cePolyTregs will be kept in a monitored freezer in vapor phase liquid nitrogen (LN₂) until the time of infusion. Stability after thawing is 4 hours. The long-term stability of cePolyTregs in LN₂ freezers is provided in the current Investigator's Brochure.

cePolyTregs will be prepared and administered under sterile conditions according to the Cell Therapy Manual. The cells will be thawed at the bedside using a water bath or comparable device maintained at 34°C to 38°C by trained personnel. There should be no frozen clumps left in the container at the time it is infused. If the cePolyTregs cell product appears to be damaged or the bag appears to be compromised, it should not be infused, and the site should notify HICTF and the GMP facility immediately.

